12 STUDY PATIENTS

12.1 Subject Disposition

Enrollment and disposition will be summarized by treatment group and overall for all randomized subjects. All enrolled subjects are defined as those who signed the informed consent form. The subject disposition summary will include:

- Number of randomized subjects
- Number of subjects randomized but not dosed
- Number of subjects in the MITT analysis set
- Number of subjects in the safety analysis set
- Number of subjects in the PP analysis set
- Number of subjects who completed the 12-week treatment period
- Number of subjects who completed the study (i.e., completed the Week 14 visit or rolled over to Study TRCA-301E)
- Number of subjects who prematurely discontinued from the study
 - The primary reason for withdrawal from the study
- Number of subjects who entered in Study TRCA-301E

A listing of disposition will be provided for all enrolled subjects. Subjects who are excluded from MITT or PP analysis sets will be listed, along with reasons for the exclusions.

12.2 Protocol Deviations

Protocol deviations will be classified by deviation type (i.e., important) and category (e.g., eligibility criteria, out of window visit, SAE reporting, missed or out of window procedures, etc.). All deviations will be identified prior to database lock and important deviations will be presented in listing(s). Important protocol deviations (referred to in the protocol as “major protocol deviations”) are defined per ICH guidance. Important deviations will be summarized by deviation category and treatment group. Important protocol deviations will be defined for this study prior to database lock and are described in detail in the Protocol Deviation Adjudication Memo.

Protocol deviation categories include:

- Investigational product
- Informed consent
- Key eligibility criteria
- Other eligibility criteria
- SAE reporting
- Out of window procedure
- Procedure - missed or not interpretable
- Out of window visit
- Missed visit

- Restricted medications
- Randomization
- Stratification
- Blinding
- Other

12.3 Demographics and Baseline Characteristics

Demographics and baseline characteristics will be summarized for all randomized subjects. Demographic characteristics will include age, age group (< 65 or \geq 65 years), sex, race, and ethnicity. The following baseline characteristics will be summarized: baseline alkali use (Yes or No), geographic region, baseline weight, height, body mass index (BMI), baseline systolic blood pressure (SBP) and baseline SBP group (\leq 135 or $>$ 135 mmHg). In addition, the following selected baseline laboratory test results will be summarized: Screening eGFR, Screening eGFR group (< 30 or \geq 30 mL/min/1.73m²), baseline eGFR, baseline blood bicarbonate, baseline blood bicarbonate group (\leq 18 or $>$ 18 mEq/L), baseline serum potassium, baseline urine albumin to creatinine (ACR) ratio, baseline urine ACR group (< 30 mg/g; or \geq 30 mg/g and \leq 300 mg/g; or $>$ 300 mg/g), baseline serum albumin, baseline serum phosphate, and baseline serum calcium. Furthermore, baseline 5-year and 2-year kidney failure risk (%) will be calculated using the 8-variable kidney failure risk prediction equation (Tangri, et al. JAMA. 2011;305(15):1553-1559). All of the above information will be listed by subject in the following categories: demographic information, baseline characteristics, and selected baseline laboratory test results. A listing will compare the randomization stratification variables in the IRT system with the Screening eGFR group (< 30 or \geq 30 mL/min/1.73m²) and Baseline blood bicarbonate group (\leq 18 or $>$ 18 mEq/L).

12.4 Medical History

Medical history will be mapped to preferred terms and system organ classes using the Medical Dictionary for Regulatory Activities (MedDRA[®]) Dictionary (version 20.0). Selected medical history items (by preferred term), CKD etiology, and selected recurrent signs and symptoms will be summarized by treatment group. Medical history, selected medical history terms, and kidney

disease history (primary cause and recurring signs and symptoms) will be summarized for all randomized subjects and listed by treatment group and subject identification number.

13 STUDY DRUG AND OTHER MEDICATIONS

13.1 Prior and Concomitant Medications

Prior and concomitant medications (see definition in Section 11.4.2) will be summarized by treatment group using WHO DD ATC class and preferred name. These summaries will present the number and percentage of subjects using each medication. Subjects may have more than one medication within an ATC class and preferred name. At each summary level subjects are counted once if they reported one or more medications at that level. Each summary will be ordered by descending frequency of incidence of ATC class and preferred name within each ATC class.

13.2 Restricted Medications

The concomitant use of restricted medications as defined in the Study TRCA-301 protocol, Section 5.9 Table 1 will be summarized and listed separately, using the same dictionary mapping as described above or based on manual medical review. Number (%) of subjects who used new or changed dose of oral alkali and calcium supplements will be summarized. Summary of certain new/dose changed antihypertensive medications given systemically (i.e., diuretics and renin-angiotensin-aldosterone system [RAAS] inhibitors, such as angiotensin-converting enzyme [ACE] inhibitors, angiotensin II receptor blockers [ARBs], aldosterone antagonists [AAs], renin inhibitors, mineralocorticoid receptor antagonists [MRAs], β -blockers, calcium channel blockers, alpha-adrenergic antagonists drugs, and direct vasodilators) regardless of stated indication will also be provided. Calcium supplements are defined as orally administered calcium carbonate, calcium acetate, calcium citrate, and other calcium salts taken for any indication.

13.3 Exposure to Study Drug, Study Treatment Compliance, and Dose Titration

Summaries will include the total number of packets dispensed, total number of packets consumed, total dose (g) consumed, study drug compliance, and duration (days) of exposure during the study treatment period.

Total dose (g) consumed is derived as the sum of the assigned dose level (i.e., subjects assigned to the TRC101 treatment group consumed 3 g TRC101 per packet) for all empty packets returned.

Study drug compliance (expressed in percentage) will be derived in the following way:

- Using the drug accountability data, the compliance is defined as $100\% \times$ the total number of empty packets returned divided by the total number of packets dispensed.

If a subject terminated from the study early and did not return packets, the packets dispensed at the last visit prior to termination will not be included in the calculations for study drug dosing or compliance.

The duration of study drug exposure is defined as the number of days on treatment from the first dose of study drug until the last dose of study drug. Study drug exposure will be summarized with descriptive statistics by treatment group.

Furthermore, number (%) of subjects with and without dose titration of study drug and those with dose uptitration, dose downtitration, and dose interruption during the treatment period will be summarized by treatment group and overall using subject counts, percentages and the exact 95% CI of the percentages. Number (%) of subjects who were dispensed a minimum and a maximum 0, 1, 2 or 3 study drug packets per day over various time intervals will be summarized by treatment group. Mean daily dose of study drug dispensed will also be summarized by treatment group and time interval. Denominators for percentages will be based on the number of subjects who remained active in the study during each time interval of interest.

The drug accountability information, including reasons or comments for incomplete or missed doses, will be listed in a patient listing. Subject dosing diary information will also be listed.

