5 STUDY TREATMENT(S)

5.1 Description of Treatment(s)

5.1.1 *Investigational Drug*

TRC101 is packaged in labeled packets and dispensed in cartons containing eight (8) packets each. Refer to the current version of the TRC101 Investigator's Brochure for a more detailed description of the investigational drug.

5.1.2 *Placebo*

Placebo consists of [REDACTED], National Formulary (NF) Grade, and is packaged in labeled packets and dispensed in cartons containing eight (8) packets each.

5.1.3 *Study Drug Dispensing, Packing and Labeling*

Labelled cartons of TRC101 and placebo will be shipped to the study site where they will be stored at room temperature (15 to 25 °C) in a secure location.

Study drug will be dispensed by the unblinded Pharmacist or study staff member designated for this role by the Investigator (hereafter referred to as “the Pharmacist”) according to the subject’s treatment assignment. The exact dispensing instructions will be provided to the Pharmacist by the interactive response technology (IRT) system.

The Pharmacist will be responsible for maintaining complete study drug dispensing, returning, and dosing records for each study subject enrolled at the site.

5.2 *Treatment(s) Administered*

Randomization will be performed using the IRT system. Approximately 210 subjects will be randomized in a 4:3 ratio to one of the following treatments:

- 6 g TRC101 QD (n~120)
- Placebo QD (n~90)

Subjects with blood bicarbonate values of 12 to 18 mEq/L will be randomized without restriction. Once 105 subjects with blood bicarbonate values of > 18 to 20 mEq/L at baseline (i.e., average of Screening Visit 1, Screening Visit 2, and pre-dose Day 1 values) have been enrolled, randomization may be closed to additional subjects with baseline blood bicarbonate in this range.

TRC101 or placebo will be administered orally as an aqueous suspension, QD with lunch, for 12 weeks.

The Investigator will designate an unblinded Pharmacist to dispense and account for study drug and to train subjects on study drug preparation and administration. The first dose of TRC101 or placebo will be administered at the study site in the morning with food (light meal or snack) and under the supervision of the Pharmacist after the baseline blood samples have been drawn. The Pharmacist will train the subject on how to administer the study drug in accordance with the subject dosing instructions.

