5.3 Dosing Regimen

The study drug dose titration algorithm is described in [Appendix 2](#). Dose titrations can only be performed during a clinic visit. If the dose of study drug is changed, the subject will start the new dose at lunch time on the titration day. Dose titrations should be performed on the basis of onsite i-STAT blood bicarbonate measurements only.

The study drug dose will be fixed for the first 4 weeks of the Treatment Period (during this time each subject will receive the study drug dose assigned at randomization [Baseline Visit]); no study drug dose adjustments will be permitted before the Week 4 Visit, except for subjects with elevation of blood bicarbonate ≥ 27 mEq/L. If the blood bicarbonate level is 27 to 30 mEq/L at any time during the Treatment Period through Week 11, the study drug dose will be decreased by 1 packet/day (minimum dose is 0 packets/day). Beginning at the Week 4 Visit, subjects with a blood bicarbonate level below the normal range (< 22 mEq/L) will have a blinded adjustment of the study drug dose in accordance with the titration algorithm (see [Appendix 2](#)). The study drug dose will only be titrated if NO dose changes have been made during the previous 14 days. If blood bicarbonate is confirmed to be > 30 mEq/L at any time during the study, the study drug treatment will be interrupted, no study drug will be dispensed to the subject, and the subject will be invited for a visit in approximately 1 week to retest blood bicarbonate. If blood bicarbonate decreases to < 27 mEq/L and the subject is still within the Treatment Period, study drug should be re-started at a lower dose in accordance with the titration algorithm (see [Appendix 2](#)). If blood bicarbonate is ≥ 27 mEq/L, the study drug dosing should be withheld until blood bicarbonate is < 27 mEq/L.

No dose titration will be allowed after Week 11 (i.e., 77 days after the day of the first dose). Dose titrations are blinded.

The Medical Monitor must be notified within 24 hours of confirmation of a bicarbonate value > 30 mEq/L or < 12 mEq/L. Dose interruptions due to blood bicarbonate elevations should be performed on the basis of i-STAT measurements, except in unusual situations when they may be based on confirmed non-i-STAT blood bicarbonate values > 30 mEq/L, e.g., if i-STAT values cannot be obtained because the subject is hospitalized.

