5.11 Treatment Compliance

The Pharmacist will assess subjects' treatment compliance at every study visit during the 12-week Treatment Period to confirm that the subject is taking study drug according to the protocol instructions and to document compliance in the eCRF as detailed in the eCRF completion guidelines. Compliance will be assessed on the basis of the assigned study drug dose, the duration of treatment, and the quantity of dispensed and returned containers (used and unused). The dosing diary data collected from the study subjects will be used as a secondary means for assessing compliance. Supervised study drug dosing on Day 1 at the study site will occur to ensure subject compliance with dosing instructions. Subjects will be provided with a dosing diary and will be requested to record the time when study drug was taken and the number of packets taken. Subjects will be instructed to save their opened/empty (used) study drug containers and bring them to the next study visit for compliance assessment along with any unopened containers. The Pharmacist will not share any potentially unblinding information with the subject or any other party as described in [Section 5.7](#).

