7.8 Week 12 or Early Termination Visit (ET)

The following assessments will be performed at the Week 12 Visit for subjects who completed the entire Treatment Period or ET Visit for subjects who withdrew from the study early. Subjects must present to this visit in a fasted state. The last dose of study drug should be taken on Day 84 of the study, regardless of the date of the Week 12 visit; however, every effort should be made to conduct the Week 12 visit on Day 85, which is in exactly 12 weeks from Day 1 (Baseline Visit).

- Record concomitant medications
- Collect vital signs (blood pressure [in triplicate], heart rate, temperature, and respiratory rate [in triplicate])
- Collect body weight

- Perform a complete physical examination
- Perform repeated chair stand test
- Collect answers to KDQOL questions
- Record 12-lead ECG (triplicate)
- Draw fasting blood for the following assessments at local laboratory: i-STAT bicarbonate, enzymatic assay serum bicarbonate or venous blood gas bicarbonate assay, coagulation (for subjects receiving vitamin K antagonists or factor Xa inhibitors only)
- Draw fasting blood for the following assessments at central laboratory: serum chemistry panel, hematology panel, hemoglobin A1c, biomarker panel and serum pregnancy test (for women of childbearing potential only)
- Obtain urine for the following assessments at central laboratory: spot urine, urinalysis, and urine biomarker panel
- Obtain 24-hour urine sample for assessment at central laboratory
- Collect used and unused study drug containers since the previous visit and corresponding dosing diary, assess dosing compliance and perform drug accountability [to be done by the Pharmacist only]
- Record AEs
- Dietary counseling
- Schedule the next study visit

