16 CHANGES RELATIVE TO THE PROTOCOL-SPECIFIED ANALYSIS

16.1 Other Efficacy Analyses

SAP Section 14.8 contains additional efficacy and dosing analyses that were not described in the protocol as follows:

- Additional categorical thresholds of bicarbonate increase (≥ 2 mEq/L and ≥ 3 mEq/L) was added to further understand potential treatment effect on bicarbonate increase in lower ranges.
- Baseline descriptor of kidney failure risk at 2 and 5 years (i.e., Kidney Failure Risk Equation score) was added to describe baseline kidney failure risks in the study population.

- Analyses exploring the effects of starting dose and dose titration.

While the protocol specified one of the safety endpoints as “Having met the high bicarbonate dose interruption criterion (confirmed > 30 mEq/L) at any time during the Treatment Period.”, SAP Section 15.3 describes summaries of subjects who had a bicarbonate > 30 mEq/L event. Removing the “confirmed” qualifier should capture any subjects potentially meeting the high bicarbonate dose interruption criterion at any time during the Treatment Period.

17 Reference

1. Yuan Y. Sensitivity Analysis in Multiple Imputation for Missing Data, SAS Institute Inc. <http://support.sas.com/resources/papers/proceedings14/SAS270-2014.pdf>
2. Tangri, et al. A predictive model for progression of chronic kidney disease to kidney failure JAMA. 2011;305(15):1553-1559
3. Hays RD, et al. Kidney Disease Quality of Life Short Form (KDQOL-SFtm), Version 1.3: A Manual for Use and Scoring. Rand, 1997.

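### SAP 13.3 measures compliance against packets dispensed rather than packets due, so the score and the 80% per-protocol cut depend on how many packets are issued

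*SAP*

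**What the plan says.** SAP 13.3 gives one rule: "Using the drug accountability data, the compliance is defined as" 100% times "the total number of empty packets returned divided by the total number of packets dispensed". The only adjustment is for early terminators who return no packets, whose last dispensing is left out. Nothing is said about unused packets that are returned, or about days on which the algorithm holds the drug.

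Protocol 5.11 describes a broader basis: "Compliance will be assessed on the basis of the assigned study drug dose, the duration of treatment, and the quantity of dispensed and returned containers", with containers counted both used and unused. SAP 16.1 opens its list of differences with "SAP Section 14.8 contains additional efficacy and dosing analyses that were not described in the protocol as follows"; the compliance derivation does not appear anywhere in SAP 16.

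On supply, Protocol 5.1.1 states that "TRC101 is packaged in labeled packets and dispensed in cartons containing eight (8) packets each" (5.1.2 says the same of placebo), and Protocol 5.1.3 that "The exact dispensing instructions will be provided to the Pharmacist by the interactive response technology (IRT) system". Neither document states how many packets or cartons are issued at a visit. Protocol 5.12 asks subjects to return everything at each post-baseline treatment visit, whereas Appendix 1 note s speaks of collection at Week 12 or early termination, which leaves room for carry-over.

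SAP 9.2 makes compliance of at least 80% a condition for the per-protocol set. SAP 11.8 uses that set in support of the primary and secondary efficacy analyses.

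**The concern.** Compliance should compare what a subject took with what the subject was meant to take. With packets dispensed as the denominator, two kinds of unused packet look like missed doses:

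- surplus packets issued above the need for the interval;
- packets left over when the titration algorithm lowers or holds the dose between two dispensing visits.

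Two subjects with the same intake can therefore score differently, and fall on different sides of the 80% cut, because of supply alone. A subject who follows a mandated hold exactly could be excluded from the per-protocol set for doing so. Reductions and holds are triggered by high bicarbonate, which is also the efficacy variable, so exclusions of this second kind could be related to outcome. How often this happens, and whether it differs between arms, cannot be known from the documents.

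**Working it through.** There is no stated figure to reproduce: the 80% is a definition. The check is a packet count.

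**Inputs**
- Dispensing at Day 1 and Weeks 1, 2, 4, 6, 8 and 10 (Appendix 1): intervals of 7, 7, 14, 14, 14, 14 and 14 days, 84 in total.
- Last dose: "The last dose of study drug should be taken on Day 84 of the study, regardless of the date of the Week 12 visit" (Protocol 7.8).
- 3 g per packet (SAP 13.3), so the 6 g starting dose is 2 packets/day.
- 8 packets per carton (Protocol 5.1).
- Assumed, because not stated: the issue rule. Exact count and fewest whole cartons per visit are both shown. All empty packets are taken to be returned.

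**Untitrated subject at 2 packets/day**
- Packets due: 14 + 14 + 5 × 28 = 168. Neither 14 nor 28 is a multiple of 8.
- Exact-count supply: 168/168 = 100%.
- Fewest whole cartons, leftovers carried forward: 16 + 16 + 24 + 32 + 24 + 32 + 24 = 168, again 100%.
- Fewest whole cartons, no netting: 16 + 16 + 5 × 32 = 192; 168/192 = 87.5%.
- One spare carton per visit as well: 192 + 7 × 8 = 248; 168/248 = 67.7%.
- Full adherence drops below 80% once more than 168/0.80 = 210 packets are issued.

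**Meaning of the 80% cut with 192 issued.** It becomes 80/87.5 = 91.4% of packets due.

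| Days missed | Packets taken | Against 192 dispensed | Against 168 due |
|---|---|---|---|
| 7 | 154 | 80.2% | 91.7% |
| 8 | 152 | 79.2% | 90.5% |
| 16 | 136 | 70.8% | 81.0% |
| 17 | 134 | 69.8% | 79.8% |

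Subjects missing 8 to 16 days thus pass on packets due and fail on packets dispensed.

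**Fully adherent subject, one-week hold starting mid-interval, restarted at 1 packet/day.** For the Week 3 case, packets taken are 14 + 14 + 14 + 56 = 98. Packets issued are 14 + 14 + 28 + 4 × 14 = 112 with exact count, or 16 + 16 + 32 + 4 × 16 = 128 with cartons.

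| Hold at | Exact count | Whole cartons, no netting |
|---|---|---|
| Week 3 | 98/112 = 87.5% | 98/128 = 76.6% |
| Week 5 | 112/126 = 88.9% | 112/144 = 77.8% |
| Week 7 | 126/140 = 90.0% | 126/160 = 78.8% |
| Week 9 | 140/154 = 90.9% | 140/176 = 79.5% |

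**Fully adherent subject, mid-interval reduction to 1 packet/day, same weeks**
- Exact count: from 105/119 = 88.2% (Week 3, packets reissued) to 147/154 = 95.5% (Week 9, no reissue).
- Whole cartons, no new carton: 105/128 = 82.0% to 147/176 = 83.5%.
- Whole cartons, one new carton: 105/136 = 77.2% to 147/184 = 79.9%.

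**Same subjects against packets due.** The four hold cases give 98/98, 112/112, 126/126 and 140/140, all 100%. A subject who silently stops after Day 60 but attends through Week 12 gives 120/168 = 71.4%. If packets due were cut off at the actual last dose, that subject would score 120/120 = 100%, so the end date must not be the last dose taken.

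**The case against.** **No conflicting formulas.** Protocol 5.11 describes the Pharmacist's assessment at visits and gives no formula, and Protocol 8.7 only says that compliance will be summarised. This stands: the point is an unexplained omission in the SAP derivation, not two rival formulas, and no stated figure is miscalculated.

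**Possible dose-based meaning of *dispensed*.** Elsewhere SAP 13.3 speaks of packets per day dispensed, where the term follows the assigned dose. That shows loose usage, but it does not turn a total count from accountability data into packets due.

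**Unknown supply rule.** The exclusions shown need whole-carton issue and no netting. With exact-count supply every hold and reduction example passes, and with whole cartons an untitrated perfect subject still passes at 87.5%. This stands, and it is why the result is a range.

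**Narrow titration examples.** Protocol 5.3 says "Dose titrations can only be performed during a clinic visit", and a change at a scheduled dispensing visit leaves no surplus. A mid-interval change from 2 packets/day needs an ad hoc visit, because the one-week retests in Appendix 2 follow an earlier decrease or hold. This stands as a limit on frequency, although Protocol 7.11 provides for unscheduled visits for dose adjustment.

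**Small consequence.** Diary and accountability data, with reasons for missed doses, are listed, so a supply-driven low score could be spotted. Listings do not change who is in the per-protocol set.

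**Conclusion.** The concern holds. As written, the SAP 13.3 ratio omits the assigned dose and duration named in Protocol 5.11, and both the score and the 80% cut move with the quantity issued. For a perfectly adherent untitrated subject the score is 100% under exact supply or netting and 87.5% under fewest whole cartons without netting; the effective cut in the latter case is 91.4% of packets due. A fully adherent subject with a one-week mid-interval hold scores 87.5% to 90.9% or 76.6% to 79.5% under the same two issue rules.

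These figures rest on assumed issue rules. If supply is exact or leftovers are netted, the surplus effect for untitrated subjects disappears, but the SAP specifies neither. The effect is confined to the compliance summary and the supportive per-protocol analyses. The MITT primary and secondary analyses, the testing sequence and safety are untouched. The change should be made, but it is not critical.

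**What to change.** In SAP 13.3, define compliance as 100% × empty packets returned / packets due.

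- **Packets due:** the assigned packets/day summed over each day from first dose to the planned end of dosing (Day 84) or the date of formal study drug discontinuation, leaving out days on algorithm-mandated holds. The end date is not the subject's actual last dose.
- **Early terminators who return no packets:** keep the present rule by dropping that last interval from packets due.
- **Threshold:** keep 80%. It then means 80% of packets due whatever the IRT issues.
- **Consistency:** reconcile the text with Protocol 5.11 and list any remaining difference in SAP 16.

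Stating only that *dispensed* is net of unused returns would remove most of the surplus effect, but it could hide missed doses, so it is not a full substitute.

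The cost is one derivation from dispensing dates, IRT dose assignments and discontinuation dates already held. It needs a little more programming, no new data collection and no change to the titration rules.
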